**Table 5.1-6: Screening and Cycle 1 (Part 3: Nivolumab Combination Arm / 21 Day Cycle) Procedural Outline (CA008002)**

Procedure a	Pre-Screening	Screening Visit D-28 to D-1	C1D1	C1D2	C1D4 b	C1D8	C1D15	Notes
Tumor Markers (CA125 and CA19-9)			X					At the time of tumor assessments: serum CA125 for ovarian cancer and mesothelioma subjects only, serum CA19-9 for pancreatic cancer subjects only. Baseline sample collection pre-dose on C1D1.
Concomitant Treatments			X	X	X	X	X	
Adverse Event Reporting								
Clinical Complaints		X						Clinical complaints related to the disease under study must be collected within 14 days of the first dose of study drug.
Monitor for Non-SAEs			X	X	X	X	X	Non-SAEs will be collected starting with the first dose of study medication and through 100 days after discontinuation of dosing.
Monitor for SAEs		X	X	X	X	X	X	All SAEs must be collected from the date of subject's written consent until 100 days from the last dose of study drug or subject's participation in the study if the last scheduled visit occurs at a later time.
Clinical Drug Supplies								
Dose Level Assignment		X						At the completion of screening procedures and eligibility determination.
BMS-986148 Administration			X					Supplied by BMS.
Nivolumab Administration			X					Supplied by BMS. For Parts 3A and 3B only. See Section 4 for administration details. Observation in a clinical setting is required

**Table 5.1-6: Screening and Cycle 1 (Part 3: Nivolumab Combination Arm / 21 Day Cycle) Procedural Outline (CA008002)**

Procedure a	Pre-Screening	Screening Visit D-28 to D-1	C1D1	C1D2	C1D4 b	C1D8	C1D15	Notes
								for 4 hours after dose administration for Cycles 1 and 2 and 1 hour after dose administration in subsequent cycles.

a In the event multiple procedures are required at a single time point, the following is a list of procedures from highest priority to low: 1) ECG, 2) PK sampling, and 3) clinical labs.

b C1D4 visit: ± 1 day.

c Ophthalmological examination: 8-point exam (visual acuity, pupils, extraocular motility and alignment, tonometry, visual field, external examination, slit lamp examination and funduscopy) conducted at baseline and focused exams with visual acuity, slit lamp, and as indicated will be conducted at the end of Cycle 1 (pre-dose Cycle 2), every other cycle, EOT and as clinically indicated during the study.

d During Cycle 1: vital signs will be obtained before the BMS-986148 infusion and then every 15 minutes (± 5 minutes) until 60 minutes after completion of the infusion. After Cycle 1 vital signs may be obtained pre-dose, every 30 minutes (± 10 minutes) until 30 minutes following completion of the infusion. If any vital sign is abnormal at the final check, the subject must be observed further for a period of time, as clinically indicated. The start and stop time of the study drug infusion should be documented (start of drug infusion = 0 hour).

█ C: cycle; CBC: complete blood cell (count); CRF: case report form; D: day; █  
 █ ECG: electrocardiogram; ECOG: Eastern Cooperative Oncology Group; EOT: end of treatment; fT3: free triiodothyronine; fT4: free thyroxine; Hep: hepatitis; HIV: human immunodeficiency virus; IHC: immunohistochemistry; LVEF: left ventricular ejection fraction; MUGA: multigated acquisition; PE: physical examination; PK: pharmacokinetics; RNA ribonucleic acid; SAE: serious adverse event; TSH: thyroid-stimulating hormone.

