### **1.5.2 Risk/Benefit for BMS-986148 and Nivolumab Combination Therapy**

Nivolumab has demonstrated clinical activity in subjects with advanced NSCLC, renal cell carcinoma, melanoma, and lymphomas, as well as other tumors, including ovarian, gastric, and mesothelioma. The clinical activity of nivolumab monotherapy observed to date in these malignancies suggests the potential for improved clinical outcomes relative to other approved therapies.

Nivolumab has demonstrated a manageable safety profile. The overall safety experience, when used either as a monotherapy or in combination with another therapeutic, is based on experience in approximately 8,600 subjects treated to date. There is no pattern in the incidence, severity, or causality of AEs with respect to nivolumab dose level. The most common AEs (as of 01 July

2016) include fatigue, rash, pruritus, diarrhea, and nausea. Side effects of nivolumab therapy may include those associated with immune-mediated activation, such as pneumonitis, thyroiditis, and hepatitis. Most of these events resolved with immune-modulating medication. To mitigate risk from serious immune-mediated AEs, subject management algorithms for nivolumab-related AEs from prior collective nivolumab experience have been included ([Appendix 3](#)).

There is potential for overlapping toxicity between clinical findings of BMS-986148 and nivolumab-related hepatotoxicity, infusion-related reactions, and peripheral neuropathy.

Elevation of the liver transaminases were the DLTs noted in 4 of the 10 subjects treated with BMS-986148 at 1.6 mg/kg Q3W. This dose is above the MTD, and no additional subjects will be treated at this dose. At the selected starting dose of BMS-986148 of 0.8 mg/kg IV Q3W, no DLTs were observed in the 4 evaluable subjects. However, the incidence of nivolumab-related hepatitis is quite low (approximately 1%). Subjects in this study receiving BMS-986148 monotherapy or BMS-986148 and nivolumab combination therapy will be monitored closely for any LFT abnormalities via laboratory assessments and frequent assessment for the development of symptoms. Study drug will be discontinued for any significant LFT abnormalities.

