### **BMS-986148 Administration**

The administration of the entire bag contents (or the amount needed if the total dose is less than 50 mg) should be infused within approximately 60 minutes through an IV infusion set (sterile, nonpyrogenic, low protein binding, polyethersulfone 0.2- $\mu$ m in-line filter) (supplied by the site). Care must be taken to ensure the sterility of the prepared solution, as the drug product does not contain antimicrobial preservatives or bacteriostatic agents. Equilibration to room temperature is recommended for the drug product, infusion fluid, and their combination prior to administration.

Reconstituted (with sterile water for injection) and diluted solutions (in normal saline) of BMS-986148-01 for injection are stable for up to 24 hours, at either refrigerated conditions, 2°C to 8°C (36°F to 46°F), and light protected or 4 hours at room temperature conditions, 15°C to 25°C (59°F to 77°F), under ambient light. The constituted vial and diluted bag should not be shaken. Infusion of BMS-986148-01 injection must be completed within 24 hours of dilution. The start of drug infusion equals 0 hour.

For subjects receiving nivolumab in combination with BMS-986148, subjects should receive nivolumab at a dose of 360 mg as a 30-minute infusion on Day 1 of each 21-day treatment cycle until disease progression, unacceptable toxicity, withdrawal of consent, or the study ends, whichever occurs first.

For combination treatment in Part 3, BMS-986148 will be administered as an infusion up to 60 minutes. The infusion line containing BMS 986148 should be flushed with an appropriate amount of diluent to ensure that the entire dose is administered and that the infusion line is cleared of any remaining BMS-986148. The nivolumab dose would then be infused not less than 30 minutes from the completion of the BMS-986148 infusion, which would then be infused over a period of 30 minutes.

The start and stop time of the all study therapy infusions and any interruptions or infusion rate reductions should be documented.

Refer to the IB for additional details about BMS-986148.

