Monitor for Non-SAEs			X	X	X	X	X	Non-SAEs will be collected starting with the first dose of study medication and through 60 days after discontinuation of dosing.
Monitor for SAEs		X	X	X	X	X	X	All SAEs must be collected from the date of subject's written consent until 60 days from the last dose of study drug or subject's participation in the study if the last scheduled visit occurs at a later time.
Clinical Drug Supplies								
Dose Level Assignment		X						At the completion of screening procedures and eligibility determination.
BMS-986148 Administration			X					Those supplied by BMS.

a In the event multiple procedures are required at a single time point, the following is a list of procedures from highest priority to low: 1) ECG, 2) PK sampling, and 3) clinical labs.

b C1D4 visit: ± 1 day.

c Ophthalmological examination: 8-point exam (visual acuity, pupils, extraocular motility and alignment, tonometry, visual field, external examination, slit lamp examination and funduscopy) conducted at baseline and focused exams with visual acuity, slit lamp, and as indicated will be conducted at the end of Cycle 1 (pre-dose Cycle 2), every other cycle, EOT, and as clinically indicated during the study.

d During Cycle 1: vital signs will be obtained before the BMS-986148 infusion and then every 15 minutes (± 5 minutes) until 60 minutes after completion of the infusion. After Cycle 1, vital signs may be obtained pre-dose, every 30 minutes (± 10 minutes) until 30 minutes following completion of the infusion. If any

vital sign is abnormal at the final check, the subject must be observed further for a period of time, as clinically indicated. The start and stop time of the study drug infusion should be documented (start of drug infusion = 0 hour).

[REDACTED] C: cycle; CBC: complete blood cell (count); CRF: case report form; D: day; [REDACTED]  
[REDACTED] ECG: electrocardiogram; ECOG: Eastern Cooperative Oncology Group; EOI: end of infusion; EOT: end of treatment; IHC: immunohistochemistry; LVEF: left ventricular ejection fraction; MUGA: multigated acquisition; PE: physical examination; PK: pharmacokinetics; Q3W: every 3 weeks; QTcF: QT interval corrected by Fridericia's formula; SAE: serious adverse event.

**Table 5.1-3: Cycle 2 to Off Study Visit, Parts 1A and 2 (Q3W Dosing BMS-986148 Monotherapy Dosing / 21 Day Cycle) Procedural Outline (CA008002)**

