**Table 5.1-7: Cycle 2 to Off Study Visit (Part 3: Nivolumab Combination Arm / 21 Day Cycle) Procedural Outline (CA008002)**

Procedure a	C2 and C3			C4					C5 and Beyond	EOT	Follow-up (30, 60, and 100 Days after Last Dose)	Survival Follow-up b	Notes
	D1	D 8	D1 5	D1	D2	D4 c	D8	D15	D1		(±5 days)	(±2 weeks)	
Ophthalmological Examination d	Start of Cycle 2, every 2 cycles thereafter and as clinically indicated									X			Performed by ophthalmologist or locally qualified personnel. Any abnormality must be discussed with the medical monitor prior to dosing. Ophthalmological exams can be done up to 72 hours prior to dosing.
Physical Measurements	X			X					X	X	X		Weight only.
Vital Signs e	X	X	X	X					X	X	X		See note in screening procedures.
ECGs	X			X	X		X		X	X	X		See note in screening procedures.
Echocardiogram	X			See notes						X			Echocardiogram done at the start of Cycle 2 and Cycle 3, then every 3 cycles thereafter, and as clinically indicated for the evaluation of pericardial effusion. On treatment echocardiogram exams may be done up to 72 hours prior to dosing.
Laboratory Tests	X	X	X	X		X			X	X	X		See note in screening procedures and Section 5.3.1 .

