**Table 5.1-7: Cycle 2 to Off Study Visit (Part 3: Nivolumab Combination Arm / 21 Day Cycle) Procedural Outline (CA008002)**

Procedure a	C2 and C3			C4					C5 and Beyond	EOT	Follow-up (30, 60, and 100 Days after Last Dose)	Survival Follow-up b	Notes
	D1	D 8	D1 5	D1	D2	D4 c	D8	D15	D1		(±5 days)	(±2 weeks)	
Nivolumab Administration	X			X					X				Supplied by BMS. For Parts 3A and 3B only. See Section 4 for administration details. Observation in a clinical setting is required for 4 hours after dose administration for Cycles 1 and 2 and 1 hour after dose administration in subsequent cycles.
Other													
Survival Follow-up												X i	

a In the event multiple procedures are required at a single time point, the following is a list of procedures from highest priority to low: 1) ECG, 2) PK sampling, and 3) clinical labs.

b In the Survival Follow-up, subjects discontinuing study drug prior to 2 years will be followed for up to 2 years from first dose of study drug. Subjects treated for > 2 years will be followed for 6 months after EOT.

c C4D4: ± 1 day.

d Ophthalmological examination: 8-point exam (visual acuity, pupils, extraocular motility and alignment, tonometry, visual field, external examination, slit lamp examination and fundoscopy) conducted at baseline and focused exams with visual acuity, slit lamp, and as indicated will be conducted at the end of Cycle 1 (pre-dose Cycle 2), every other cycle, EOT and as clinically indicated during the study.

e Vital signs will be obtained before the BMS-986148 infusion and then every 30 minutes (± 10 minutes) until 30 minutes following completion of the last infusion. If any vital sign is abnormal at the final check, the subject must be observed further for a period of time, as clinically indicated. The start and stop time of the study drug infusion should be documented (start of drug infusion = 0 hour).

f Only anti-cancer treatments.

- g Only at the 60- and 100-day follow-up visits, unless discontinued for disease progression.
- h Subjects with SD, PR, or CR at the last clinical follow-up visit should undergo tumor assessment via CT/MRI scans at least every 3 to 4 months during the Survival Follow-up (Section 8.3.2.2) phase until progression.

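### On Cycle 1 Day 1 of Part 3, serial vital signs are timed from BMS-986148 alone, so no reading that day is nominally scheduled after the first nivolumab infusion

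*Protocol*

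**What the plan says.** Protocol Table 5.1-6 covers screening and Cycle 1 for Part 3. Its footnote d requires vital signs to be "obtained before the BMS-986148 infusion and then every 15 minutes (± 5 minutes) until 60 minutes after completion of the infusion". BMS-986148 is the only infusion named in that sentence. The monotherapy Q3W table (Table 5.1-2, footnote d) has the same schedule: "every 15 minutes (± 5 minutes) until 60 minutes after completion of the infusion". Footnote d of Table 5.1-6 adds a safeguard at the end of the series: "If any vital sign is abnormal at the final check, the subject must be observed further".

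On the order of dosing, Section 4.3 (BMS-986148 Administration) states: "The nivolumab dose would then be infused not less than 30 minutes from the completion of the BMS-986148 infusion". Nivolumab then runs for 30 minutes. No maximum gap is given.

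For Part 3 from Cycle 2, Table 5.1-7 footnote e takes readings every 30 minutes (±10) "until 30 minutes following completion of the last infusion". Table 5.1-8 footnote d ends retreatment readings at the same point.

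Other monitoring is in Section 4.3 (Nivolumab Preparation) and the nivolumab row of Table 5.1-6: careful monitoring for infusion reactions during nivolumab, and 4 hours of clinic observation after each of the first two doses. Neither place gives times for vital signs.

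**The concern.** The first combination dose is when a reaction to nivolumab given after BMS-986148 would first appear. Section 1.5.2 recognises the "potential for overlapping toxicity between clinical findings of BMS-986148 and nivolumab-related hepatotoxicity, infusion-related reactions, and peripheral neuropathy". Yet the Day 1 schedule reads as if only one drug were given. Its last check, which decides whether an abnormal value calls for longer observation, nominally falls at or before the end of nivolumab.

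Cycle 1 is otherwise the more intensive cycle, with 15-minute rather than 30-minute intervals. For the period after nivolumab the order is reversed: later cycles have scheduled readings and the first exposure has none. At stake is how consistently sites record vital signs after the first nivolumab dose.

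**Working it through.** The plan states no figure for this point, so there is none to reproduce. The check is timeline arithmetic.

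**Inputs**
- T0 = completion of the BMS-986148 infusion. Its own duration (up to 60 minutes) cancels, because the readings and nivolumab are both timed from its completion.
- Last nominal Cycle 1 reading: T0 + 60 (Table 5.1-6 footnote d). The interval tolerance is ±5 minutes, taken here to apply to the last reading too.
- Gap from T0 to the start of nivolumab: g ≥ 30 minutes (Section 4.3).
- Nivolumab duration: 30 minutes (Section 4.3).

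**Formulas**
- End of nivolumab = T0 + g + 30.
- Scheduled time after nivolumab = 60 − (g + 30) = 30 − g, which is zero or negative for every g ≥ 30.
- The same with the tolerance = 65 − (g + 30) = 35 − g, which is positive only for g < 35 and at most 5 minutes (at g = 30).
- Nivolumab minutes inside the nominal window = max(0, 60 − g).

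| Gap g (min) | Nivolumab runs | Last nominal reading relative to end of nivolumab | Nivolumab minutes covered | Nominal readings after nivolumab |
|---|---|---|---|---|
| 30 | T0+30 to T0+60 | at the end | 30 of 30 | 0 |
| 45 | T0+45 to T0+75 | 15 min before | 15 of 30 | 0 |
| 60 | T0+60 to T0+90 | 30 min before | 0 of 30 | 0 |

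Only the 30-minute minimum is documented. The rows for 45 and 60 minutes show a range and are not a forecast of practice.

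**Comparison with later cycles.** Table 5.1-7 footnote e, read literally, ends at T0 + g + 30 + 30 = T0 + g + 60, which is T0 + 90 at g = 30. That is 30 minutes of scheduled coverage after nivolumab from Cycle 2, against none on Cycle 1 Day 1.

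**The case against.** The strongest reply is that the subject is already watched. Section 4.3 requires monitoring during nivolumab and at least 4 hours in clinic after the first two doses. Section 1.5.2 says subjects will be monitored during the first combination cycle. Section 3.4.2 gives graded instructions for infusion reactions, including staying at the bedside until recovery. At the minimum gap, scheduled readings span the whole nivolumab infusion. Section 1.5.2 also describes nivolumab infusion reactions as uncommon and reports none with BMS-986148 to 01 July 2016. Details of nivolumab administration are referred to the Investigator's Brochure and/or Pharmacy Manual, which are not among the documents and may set reading times. All of this stands and limits the consequence. None of the text available schedules a Day 1 reading after nivolumab.

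Three stronger readings are tempting, and the documents do not support them.

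- *That no vital signs follow the first nivolumab dose until Cycle 2.* Table 5.1-6 marks vital signs on Cycle 1 Days 8 and 15. The gap is confined to Day 1.
- *That the later-cycle rule is unsettled.* Footnote d of Table 5.1-6 has its own later-cycle sentence ("After Cycle 1 vital signs may be obtained pre-dose"), which ends 30 minutes after a single infusion, and the vital-signs row of Table 5.1-7 says "See note in screening procedures". But the Notes entry for vital signs in Table 5.1-6 covers what is measured and the rest beforehand, with no timing. Table 5.1-1 assigns Cycle 2 onward to Table 5.1-7, whose footnote e is worded as a requirement, whereas footnote d's sentence is permissive. Footnote e therefore governs. Its end-point phrase also appears in the monotherapy tables (5.1-3, 5.1-4 and 5.1-5), so it is weak evidence that nivolumab was deliberately considered, but on a two-infusion day its literal meaning includes nivolumab.
- *That dose-limiting toxicity calls, stopping rules or endpoints are affected.* Nothing in the documents shows this. Section 8.4.3 only lists vital signs.

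**Conclusion.** The point holds for Cycle 1 Day 1 of Part 3. As written, zero nominal readings follow the first nivolumab infusion at any permitted gap. The tolerance can give at most one, within 5 minutes of the end, and only for gaps under 35 minutes. Nivolumab coverage falls from 30 of 30 minutes at a 30-minute gap to none at 60 minutes.

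This rests on reading the end point in footnote d as the end of BMS-986148, the only infusion its sentence names. It is a gap in scheduled vital signs at first combination exposure, not in overall monitoring. It is a low-cost improvement rather than a serious fault.

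**What to change.** In Table 5.1-6 footnote d, continue Cycle 1 Day 1 vital signs every 15 minutes (±5) until at least 30 minutes after completion of the last infusion, naming nivolumab. This matches the end point of Table 5.1-7 footnote e. Alternatively, run them to 60 minutes after nivolumab to keep the existing Cycle 1 window. Either way the final check then follows nivolumab. As tidying only, make footnote d's later-cycle sentence refer to the last infusion as well.

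The cost is a wording change and a few more readings per subject, counted here with readings aligned to T0 (an assumption):

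| Gap g (min) | Extra readings, 30-minute version | Extra readings, 60-minute version |
|---|---|---|
| 30 | 2 (T0+75, T0+90) | 4 (T0+75 to T0+120) |
| 45 | 3 (T0+75 to T0+105) | 5 (T0+75 to T0+135) |
| 60 | 4 (T0+75 to T0+120) | 6 (T0+75 to T0+150) |

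The readings after nivolumab fall in the first 30 or 60 of the 240 minutes that the subject must already spend in clinic.

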**Table 5.1-7: Cycle 2 to Off Study Visit (Part 3: Nivolumab Combination Arm / 21 Day Cycle) Procedural Outline (CA008002)**

Procedure a	C2 and C3			C4					C5 and Beyond	EOT	Follow-up (30, 60, and 100 Days after Last Dose)	Survival Follow-up b	Notes
	D1	D 8	D1 5	D1	D2	D4 c	D8	D15	D1		(±5 days)	(±2 weeks)	
Safety Assessments													
Targeted PE	X	X	X	X						X	X	X	To include signs and symptoms of peripheral neuropathy and ocular toxicity. Any ocular toxicity requires ophthalmologist consultation and discussion with medical monitor as appropriate. If a subject shows pulmonary-related signs (hypoxia, fever) or symptoms (eg, dyspnea, cough, and fever) consistent with possible pulmonary AEs, the subject should be immediately evaluated to rule out pulmonary toxicity, according to the suspected pulmonary toxicity management algorithm in the nivolumab IB.

**Table 5.1-7: Cycle 2 to Off Study Visit (Part 3: Nivolumab Combination Arm / 21 Day Cycle) Procedural Outline (CA008002)**

Procedure a	C2 and C3			C4					C5 and Beyond	EOT	Follow-up (30, 60, and 100 Days after Last Dose)	Survival Follow-up b	Notes
	D1	D 8	D1 5	D1	D2	D4 c	D8	D15	D1		(±5 days)	(±2 weeks)	
Ophthalmological Examination d	Start of Cycle 2, every 2 cycles thereafter and as clinically indicated									X			Performed by ophthalmologist or locally qualified personnel. Any abnormality must be discussed with the medical monitor prior to dosing. Ophthalmological exams can be done up to 72 hours prior to dosing.
Physical Measurements	X			X					X	X	X		Weight only.
Vital Signs e	X	X	X	X					X	X	X		See note in screening procedures.
ECGs	X			X	X		X		X	X	X		See note in screening procedures.
Echocardiogram	X			See notes						X			Echocardiogram done at the start of Cycle 2 and Cycle 3, then every 3 cycles thereafter, and as clinically indicated for the evaluation of pericardial effusion. On treatment echocardiogram exams may be done up to 72 hours prior to dosing.
Laboratory Tests	X	X	X	X		X			X	X	X		See note in screening procedures and Section 5.3.1 .

**Table 5.1-7: Cycle 2 to Off Study Visit (Part 3: Nivolumab Combination Arm / 21 Day Cycle) Procedural Outline (CA008002)**

Procedure a	C2 and C3			C4					C5 and Beyond	EOT	Follow-up (30, 60, and 100 Days after Last Dose)	Survival Follow-up b	Notes
	D1	D 8	D1 5	D1	D2	D4 c	D8	D15	D1		(±5 days)	(±2 weeks)	
													Lab tests can be performed up to 24 hours prior to dosing. C4D4 (CBC only) collection to be time matched with PK collection pre-dose.
Tumor Biopsy (Fresh) (Mandatory) - Part 3B Only	X												C2D1 (±3 days). For 10 ovarian cancer subjects and 10 gastric cancer subjects who provided pre-treatment biopsies.
Tumor Biopsy (Fresh) (Optional) - Part 3B Only	X												C2D1 (±3 days). For subjects with indications other than ovarian cancer and gastric cancer.
Thyroid Function	X								Odd cycles				TSH with reflexive fT3 and fT4 to be done every 6 weeks.
Pregnancy Test	X			X					X	X	X		
Concomitant Treatments	X	X	X	X	X	X	X	X	X	X	X f		
Adverse Event Reporting													
Monitor for Non-SAEs	X	X	X	X	X	X	X	X	X	X	X		Collected continuously during the treatment period and for a minimum of 100 days following discontinuation of

